8.4 Treatment Compliance

Patient compliance with study medication will be assessed at each visit. Compliance will be assessed by direct questioning and counting returned tablets/capsules. Deviations from the prescribed dosage regimen should be recorded in the CRF. A patient dosing diary will be used to capture dose information for LY3214996 and abemaciclib.

The patient must take $\geq 80\%$ of the intended doses in each cycle to be deemed compliant with study drug administration. Similarly, a patient may be considered noncompliant if he or she is judged by the investigator to have intentionally or repeatedly taken more than the prescribed amount of drug(s). Potential discontinuation of a patient due to study drug noncompliance will be discussed between the treating physician and the principal investigator before the final determination is made to discontinue the patient.

8.4.1 Evaluable Patients

Patients who withdraw from the study before receiving study drug will be replaced and will not be included in the safety or efficacy assessments. Safety analyses will be conducted on all patients who have received at least 1 dose of study drug, regardless of whether they are deemed evaluable for anti-tumor activity.

Patients evaluable for anti-tumor activity will comprise all patients who receive at least one dose of trial drug. Patients who have clinical progression prior to first disease evaluation will discontinue therapy due to progressive disease and not be replaced. Patients who are not evaluable for anti-tumor activity (e.g., study discontinuation due to patient decision before first scan) may be replaced upon consultation with the principal investigator to ensure adequate tumor response data.

8.5 Preparation/Handling/Storage/Accountability

LY3214996 will be supplied as 100-mg capsules for oral consumption. LY3214996 should be stored within the temperature range stated on the label. Investigators should instruct patients to store the capsules at home in the original container and to keep out of the reach of children. Capsules should not be opened, crushed, or dissolved.

Abemaciclib will be supplied as 50-mg tablets and should be stored within the temperature range stated on the label. Investigators should instruct patients to store the capsules at home in the original container and to keep out of the reach of children. Tablets should not be opened, crushed, or dissolved.

8.6 Concomitant Therapy

No other chemotherapy, radiotherapy immunotherapy, cancer related hormone therapy, or experimental drugs, or herbal supplements intended to treat cancer will be permitted while the patients are on this study. An exception will be made for the following circumstances:

- Prostate cancer patients continuing GnRH agonist therapy or breast cancer patients continuing antiestrogen therapy (for example, an aromatase inhibitor).
- Patients on stable doses of bisphosphonates or denosumab are allowed to continue. These agents should not be initiated within the 2 weeks prior to study enrollment or at any point while on the study

In addition, any disease progression requiring other forms of specific antitumor therapy will also necessitate early discontinuation from the study. Replacement hormone therapy initiated before study entry will be allowed.

In vitro data suggests potential inhibition of CYP3A4-mediated metabolism by LY3214996, therefore use of concomitant therapy with sensitive substrates of CYP3A4, particularly those that also have a narrow therapeutic range, should be used with caution for all patients in Study CTO-IUSCC-0730. Concomitant therapy with sensitive substrates of CYP3A4 must be avoided ([Appendix 5](#)).

In vitro, LY3214996 was an inducer of CYP2D6 and CYP3A5 messenger ribonucleic acid. The clinical relevance of the in vitro induction of CYP2D6 and CYP3A5 by LY3214996 is currently unknown. Caution should be used when using concomitant therapy with CYP2D6 and CYP3A5 substrates as the metabolism of such drugs may be induced.

In vitro data indicates that the major cytochrome P450 involved in the clearance of LY3214996 is CYP3A (~88%). Clinical studies have demonstrated that the major route of abemaciclib clearance is through CYP3A metabolism. Therefore, patients are not allowed to have any concomitant medications that are moderate or strong inhibitors (that is, grapefruit juice,

ketoconazole, etc.) or inducers of CYP3A4. Please refer to Appendix 5 for a list of contraindicated medications. Because the lists of these agents are constantly changing, it is important to regularly consult a frequently-updated medical reference for a list of drugs to avoid.

Abemaciclib and its major metabolites inhibit the efflux transporters P-glycoprotein and breast cancer-resistant protein and the renal transporters organic cation transporter 2, multidrug and toxin extrusion protein 1 (MATE 1), and MATE2-K at clinically relevant concentrations. Therefore, substrates of these transporters such as metformin and those with a narrow therapeutic index such as digoxin and dofetilide should be substituted or avoided if possible.

All premedication, supportive care and concomitant medication must be reported on the electronic case report form (eCRF) at each visit.

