8.6.1.3 Supportive Management Recommendations for Nausea and Vomiting

Approximately 90% of patients have experienced nausea and/or vomiting due to LY3214996, which in a limited number of cases has led to more severe adverse events (i.e., dehydration, acute kidney injury). Therefore, patients will be required to receive antiemetic prophylaxis in cycle 1, in an effort to improve patient safety and reduce the incidence of these events. Recommended antiemetic treatment should follow current guidelines for high/moderate emetic risk agents, such as consensus-based guidelines from the National Comprehensive Cancer Network, but is left to investigator’s discretion based on patient characteristics and local medical practices.

Current recommendation for antiemetic treatment consists of a 5-HT₃ receptor antagonist and should be given prior to starting study drug (continue daily, choose 1):

- Ondansetron 8-16 mg (total dose) PO daily
- Dolasetron 100 mg PO daily, as needed

Breakthrough treatment can be given by adding 1 agent from a different drug class to the current regimen (i.e., olanzapine 5-10 mg PO daily, dexamethasone 12 mg PO/IV daily).

In the event that the investigator believes concomitant antiemetic medication is not necessary in cycles 2+, the antiemetic regimen may be discontinued.

Caution should be taken when administering medications that are metabolized by CYP3A4 when given with LY3214996 due to the potential inhibition of CYP3A4 metabolism by LY3214996 that could result in increased exposures of the co-medications. If possible, alternate medications that are not reliant on CYP3A4 metabolism for elimination should be utilized whenever possible.

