Appendix 5. Sensitive CYP3A Substrates and Narrow Therapeutic Range Drugs

The information in this table is provided for guidance to investigators and does not preclude the use of these medications if clinically indicated.

Strong Inducers of CYP3A

Carbamazepine
Dexamethasone
Phenobarbital/phenobarbitone
Phenytoin
Rifapentine
Rifampin
Rifabutin
St John's wort

Moderate Inducers of CYP3A

Bosentan
Lenisurad
Modafinil
Primidone
Telotristat ethyl

Strong Inhibitors of CYP3A

Aprepitant
Ciprofloxacin
Clarithromycin
Conivaptan
Diltiazem
Erythromycin
Fluconazole
Itraconazole
Ketoconazole
Nefazodone
Posaconazole
Troleandomycin
Verapamil

This table is prepared to provide examples of clinical CYP3A-sensitive substrates and narrow therapeutic range drugs that are CYP3A substrates and is not intended to be an exhaustive list. Concomitant therapy with sensitive substrates of CYP3A4, particularly those that also have a narrow therapeutic range, should be used with caution for all patients.

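### Section 8.6 bars moderate or strong CYP3A4 inhibitors and inducers, but Appendix 5 permits the listed drugs if clinically indicated, and two supportive-care sections lead to drugs on that list

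*Combined protocol and SAP*

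**What the plan says.** Section 8.6 gives its reason first. In vitro, CYP3A accounts for about 88% of LY3214996 metabolism by cytochrome P450. For abemaciclib, "Clinical studies have demonstrated that the major route of abemaciclib clearance is through CYP3A metabolism". It concludes that "patients are not allowed to have any concomitant medications that are moderate or strong inhibitors", naming grapefruit juice and ketoconazole as examples, and the sentence goes on to cover inducers. It then points to the appendix: "Please refer to Appendix 5 for a list of contraindicated medications".

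Appendix 5 is titled "Sensitive CYP3A Substrates and Narrow Therapeutic Range Drugs". Its first sentence describes the table as guidance that "does not preclude the use of these medications if clinically indicated". The readable content is three lists: strong inducers, moderate inducers and strong inhibitors. The closing note describes something else: "This table is prepared to provide examples of clinical CYP3A-sensitive substrates and narrow therapeutic range drugs that are CYP3A substrates".

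Two supportive-care sections bear on the same list:

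- Section 8.6.1.3 allows breakthrough antiemetic treatment with one added agent, for example "olanzapine 5-10 mg PO daily, dexamethasone 12 mg PO/IV daily". Appendix 5 puts dexamethasone under "Strong Inducers of CYP3A".
- Section 8.6.1.2 requires broad-spectrum antibiotics when diarrhea is severe or comes with fever or severe neutropenia, with fluoroquinolones as the example. Appendix 5 lists ciprofloxacin as a strong inhibitor.

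On sensitive CYP3A4 substrates, one sentence of Section 8.6 asks for caution and the next says that they are to be avoided.

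**The concern.** The bar in Section 8.6 protects exposure to both study drugs. A site that follows Appendix 5, Section 8.6.1.3 or Section 8.6.1.2 as written can give a drug that Section 8.6 forbids and still believe that it is complying. An inhibitor could raise exposure and add toxicity; an inducer could lower exposure and reduce activity. The substrate wording concerns a different risk, namely exposure to the co-medication.

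The conflict also leaves no clear basis for calling such use a protocol deviation. Section 8.6 has concomitant medication recorded on the eCRF, which shows the use afterwards but does not prevent it.

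**Working it through.** No formula applies. The check sets the instructions side by side.

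| Item | Section 8.6 | Elsewhere |
|---|---|---|
| Drugs listed in Appendix 5 | Not allowed; the list is called contraindicated | Appendix 5: usable if clinically indicated |
| Ketoconazole | Barred by name | Appendix 5: on the list, under the permissive sentence |
| Dexamethasone | Barred as an inducer | Appendix 5: strong inducer. Section 8.6.1.3: optional breakthrough antiemetic, 12 mg daily |
| Ciprofloxacin | Barred as an inhibitor | Appendix 5: strong inhibitor. Section 8.6.1.2: its class is the example of a required antibiotic |
| Sensitive CYP3A4 substrates | Caution, then avoidance, in adjacent sentences | Appendix 5: caution |

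1. **Extent.** The readable entries in Appendix 5 are 8 strong inducers, 5 moderate inducers and 13 strong inhibitors: 8 + 5 + 13 = 26. Every one is barred by Section 8.6 and permitted under the opening sentence of Appendix 5. Entries may have been lost in reading the PDF, so 26 describes only the readable text.

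2. **Grammar of the bar.** It could be asked whether the strength qualifier in Section 8.6 applies to inducers as well as inhibitors. The answer does not matter here. Appendix 5 classes dexamethasone as a strong inducer, and the other listed inducers are strong or moderate, so all are barred on either reading.

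3. **Does Section 8.6.1.3 warn about dexamethasone?** Its CYP3A4 caution concerns LY3214996 raising exposure to a co-medication. It does not address a co-medication that speeds clearance of the study drugs.

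4. **Would the study drugs be on hold anyway?**
   - For nausea and vomiting, the Appendix 4 holds start at Grade 2 and apply after optimal antiemetic therapy. A breakthrough agent can therefore be given while both drugs continue.
   - For diarrhea, Appendix 4 holds both drugs from Grade 2, so much of the antibiotic use would begin during a hold. That hold ends when diarrhea returns to Grade 1, not when the antibiotic course ends. Section 8.6.1.2 also reaches diarrhea with fever or severe neutropenia, and for neutropenia Appendix 4 never holds LY3214996.

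5. **Is there an exception?** No section exempts dexamethasone, ciprofloxacin or short courses from the Section 8.6 bar.

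6. **How often would it arise?** Section 8.6.1.3 says that roughly 90% of patients have had nausea and/or vomiting due to LY3214996, so its advice is likely to be consulted. The rate of breakthrough antiemetic use is not given.

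**The case against.** The strongest reply is that the operative rule is clear. Section 8.6 states the bar and its reason in the body of the protocol and tells sites to check a current drug reference, while Appendix 5 calls itself guidance and not exhaustive. This does not settle the conflict. A current reference tells a site which drugs fall in a class; it does not say whether the bar or the clinical-indication exception prevails.

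A second reply is that Appendix 5 may have lost a substrate table in the PDF reading. Its title and closing note fit such a table, and the permissive sentence may have been written for it. That is a fair caution. A reader might infer that the protocol contains no substrate list at all, and the documents as read cannot support that. But lost content would not remove the permissive sentence that stands directly above the inhibitor and inducer lists, nor the listing of dexamethasone and ciprofloxacin.

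A third reply is that nobody is told to give either drug. This stands. Dexamethasone is one of two optional examples, the antiemetic regimen is left to the investigator, and an antibiotic other than ciprofloxacin would satisfy Section 8.6.1.2. A reader might infer that the protocol directs sites to give barred drugs; it does not. What remains is that it suggests one by name and the class of another, without a warning.

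On substrates, a reader might count Section 8.6.1.3 as a further contradiction. It is not a clean one: it concerns any drug metabolized by CYP3A4, and it prefers alternatives where possible. The clear clash is between the two adjacent sentences in Section 8.6.

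**Conclusion.** The point holds as an inconsistency in conduct and safety instructions that should be corrected. It affects all 26 readable Appendix 5 entries, with one named drug (dexamethasone) and one drug reached through its class (ciprofloxacin) in the supportive-care sections, plus one pair of conflicting sentences on substrates. The first part rests on reading the opening sentence of Appendix 5 as applying to the lists below it, which is how a site would read it.

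A reader might go further and infer that exposure will be materially altered or the response rate biased. The documents do not support that. They give no interaction strength for any listed drug and no frequency of use. The phase 1 results with abemaciclib 150 mg twice daily (Table 3.1) show DLTs in 1 of 6, 2 of 7 and 3 of 4 evaluable patients at LY3214996 200, 400 and 600 mg daily. That fits more toxicity at higher exposure, but the counts are small and measure no drug interaction. The sample size and the ORR test are unaffected.

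**What to change.** - **Governing rule:** state that Section 8.6 governs.
- **Appendix 5:** remove the permissive sentence for inhibitors and inducers, or limit it to substrates. Correct the title and closing note to match the lists, with the same change in the list of appendices.
- **Section 8.6.1.3:** replace dexamethasone with an agent not on the Appendix 5 list (olanzapine is already named), or write an explicit short-course exception in both Sections 8.6 and 8.6.1.3.
- **Section 8.6.1.2:** specify a broad-spectrum antibiotic not on the list, for example by excluding ciprofloxacin, or hold the study drugs while a listed one is given.
- **Substrates:** keep one instruction for sensitive CYP3A4 substrates in Section 8.6.

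The cost is a wording amendment to three sections, one appendix and the list of appendices. Sample size, visit schedule and analysis do not change.

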8.6.1 Supportive Care

Patients should receive full supportive care. Patients are instructed to maintain adequate oral hydration at home, in order to prevent dehydration secondary to vomiting and diarrhea. During visits, patients should be evaluated for signs and symptoms of dehydration and, if necessary, intravenous hydration should be implemented at the discretion of the investigator. American Society of Clinical Oncology (ASCO) guidelines (Smith et al. 2015) should be followed for patients requiring support with granulocyte-colony stimulating factor (G-CSF). If G-CSF is required, study therapy should be held. Patients should not receive G-CSF prophylactically in the first cycle of therapy.

If clinically indicated at any time during the study, packed red blood cell transfusions may be used according to ASCO guidelines (Rizzo et al. 2008). Prophylactic antibiotic treatment should be consistent with ASCO guidelines (Flowers et al. 2013).

All concomitant medications should be recorded throughout the patient's participation in the study.

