8.6.1.4 Growth Factor Therapy

Growth factors should not be administered to a patient to satisfy study inclusion criteria. Growth factors may be administered in accordance with ASCO guidelines (Smith et al. 2015). Dosing of abemaciclib and LY3214996 must be suspended if the administration of growth factors is required and must not be recommenced within 48 hours of the last dose of growth factors having been administered. Following the administration of growth factors, the dose of abemaciclib must be reduced by 1 dose level on recommencement, if a dose reduction for the specific event necessitating the use of the growth factors has not already occurred.

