Appendix 4. Dose Modification of LY3214996 & Abemaciclib

Neutropenia	Abemaciclib	LY3214996
≤ Grade 1/2	No change in dose.	No change in dose.
Grade 3	Hold* until ≤ Grade 2. Resume at same dose level.	No change in dose.
Recurrent Grade 3 or Grade 4	Hold* until ≤ Grade 2. Reduce by 1 dose level.	No change in dose.

*Patients requiring a delay of all protocol therapy > 3 weeks due to toxicity should go off protocol therapy.
 
NOTE: Use of prophylactic granulocyte colony stimulating factor is permitted per investigator discretion. Use of ASCO guidelines is recommended. Suspend therapy for at least 48 hours after the last dose of a blood cell growth factor was administered and until toxicity resolves to at least Grade 2.
		

Abbreviation: ASCO = American Society of Clinical Oncology

Thrombocytopenia	Abemaciclib	LY3214996
≤ Grade 1/2	No change in dose.	No change in dose.
Grade 3	Hold* until ≤ Grade 2. Resume at same dose level.	No change in dose.
Recurrent Grade 3 or Grade 4	Hold* until ≤ Grade 2. Reduce by 1 dose level.	No change in dose.

*Patients requiring a delay of all protocol therapy > 3 weeks due to toxicity should go off protocol therapy.
		

Anemia	Abemaciclib	LY3214996

Supportive transfusion is permitted after cycle 1, day 1 and future cycles for subjects who do not meet hemoglobin parameters for retreatment.
		
Hemoglobin	Abemaciclib	LY3214996
Grade 1/2	No change in dose	No change in dose.
Grade 3	Hold* until ≤ Grade 2. Resume at same dose level.	No change in dose.
Recurrent Grade 3 or Grade 4	Hold* until ≤ Grade 2. Reduce by 1 dose level.	No change in dose.
Patient requires administration of a blood cell growth factor	Suspend abemaciclib dose for at least 48 hours after the last dose of blood cell growth factor and until toxicity resolves to ≤Grade 2. Resume abemaciclib at next lower dose unless the dose was already reduced for the toxicity that led to the use of the growth factor.	No change in dose.

*Patients requiring a delay of all protocol therapy > 3 weeks due to toxicity should go off protocol therapy. Supportive transfusion is permitted after cycle 1, day 1 and future cycles for subjects who do not meet hemoglobin parameters for retreatment.
		

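### Appendix 4 leaves LY3214996 unchanged during growth factor for anemia, and restarts abemaciclib at full level after growth factor for a first Grade 3 neutropenia, against Section 8.6.1.4

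*Combined protocol and SAP*

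**What the plan says.** **Body text.** Section 8.6.1 (Supportive Care) states: "Patients should not receive G-CSF prophylactically in the first cycle of therapy". It adds that study therapy should be held if G-CSF is required. Section 8.6.1.4 (Growth Factor Therapy) is firmer: "Dosing of abemaciclib and LY3214996 must be suspended if the administration of growth factors is required", and dosing "must not be recommenced within 48 hours of the last dose of growth factors having been administered". It also requires abemaciclib to restart one dose level lower, unless it was already reduced for the event that led to the growth factor. It does not limit the rule to one type of growth factor.

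**Appendix 4, anemia table.** The growth-factor row tells the physician, for abemaciclib, "Suspend abemaciclib dose for at least 48 hours after the last dose of blood cell growth factor" and until recovery to Grade 2 or less, and then "Resume abemaciclib at next lower dose unless the dose was already reduced for the toxicity that led to the use of the growth factor". The LY3214996 cell in the same row says only that the dose does not change.

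**Appendix 4, neutropenia table.** For Grade 3, the abemaciclib cell reads "Hold* until ≤ Grade 2. Resume at same dose level". Recurrent Grade 3 and Grade 4 events are reduced by one level. There is no growth-factor row. The note beneath says "Use of prophylactic granulocyte colony stimulating factor is permitted per investigator discretion" and then "Suspend therapy for at least 48 hours after the last dose of a blood cell growth factor was administered", with recovery to at least Grade 2 as a further condition. It mentions neither a cycle limit nor a reduced restart dose.

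**Link between the two.** Section 8.3 refers the physician to Appendix 4 for dose adjustment. Nothing says which text governs if they differ.

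**The concern.** Dose decisions are made from the tables. A physician who treats anemia with a growth factor and reads the anemia row would keep giving LY3214996 when 8.6.1.4 says that it must stop. A physician who treats a first Grade 3 neutropenia with G-CSF and reads the neutropenia table would restart abemaciclib one level too high under 8.6.1.4. Whichever text is followed, the other makes the action a deviation.

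The second case has a lasting effect. Section 8.3 keeps a reduced dose for all remaining cycles, and abemaciclib has only two steps below the starting dose (150 to 100 to 50 mg Q12H). The choice of text therefore also settles whether one of those steps has been used.

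**Working it through.** No figure in the plan needs to be reproduced here. The check is a comparison of texts, followed by simple dose arithmetic.

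**Comparison**

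| Situation | Body text | Appendix 4 | Result |
|---|---|---|---|
| Growth factor needed for anemia: LY3214996 | 8.6.1.4: suspend; no restart within 48 h of last growth-factor dose | Anemia growth-factor row: dose unchanged | Direct contradiction |
| Growth factor needed for anemia: abemaciclib | 8.6.1.4: suspend; restart one level lower unless already reduced | Same rule, plus recovery to Grade 2 or less | Consistent |
| First Grade 3 neutropenia treated with growth factor: abemaciclib restart | 8.6.1.4: one level lower unless already reduced for that event | Grade 3 row: same level; note adds only a suspension | Different restart dose |
| Recurrent Grade 3 or Grade 4 neutropenia: abemaciclib restart | 8.6.1.4: reduction, counted once | Reduce one level | Consistent |
| Growth factor for neutropenia: suspension | 8.6.1.4: both drugs | Note: suspend therapy, no drug singled out | Consistent |
| Prophylactic G-CSF in cycle 1 | 8.6.1: should not be given | Note: permitted at discretion, no cycle stated | Limit omitted |

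The table conflict on restart dose is therefore confined to a first Grade 3 neutropenia for which growth factor is used. The paragraph after the hematologic tables has the same gap: it lets the investigator consider the same dose for a new Grade 3 episode more than 8 weeks after the last, with no growth-factor exception.

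**Size per affected patient**

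- Abemaciclib at the starting dose, Appendix 4 restart: 150 mg × 2 = 300 mg/day; × 28 = 8,400 mg per cycle.
- Abemaciclib, 8.6.1.4 restart: 100 mg × 2 = 200 mg/day; × 28 = 5,600 mg per cycle.
- Difference: 8,400 − 5,600 = 2,800 mg; 2,800 / 8,400 = 33.3%. This is one dose step and assumes full dosing with no later change.
- LY3214996 at 200 mg daily: 48 h / 24 h = 2 doses; 2 × 200 mg = 400 mg that the anemia row would let the patient take. This is a minimum, because 8.6.1.4 suspends dosing from the time growth factor is required and the 48 hours run from its last dose.

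**Number of patients**

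The documents give no growth-factor rate. Section 3.1.2.1.1 gives neutropenia of 37.1% among 132 patients (49/132 = 37.1%), grade not stated, on single-agent abemaciclib 200 mg twice daily. Table 3.2 gives related anemia in Part C, the combination, as 5 of 20 at any grade and 0 of 20 at Grade 3 or higher. Table 3.1 lists one Grade 3 anemia/thrombocytopenia DLT, but with LY3214996 200 mg twice daily, which is not the study dose. None of these measures growth-factor use at the study doses.

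**The case against.** **The texts can be read together.** The neutropenia note gives a general permission and 8.6.1 a specific limit; a physician can respect both. The limit is also worded as a recommendation. This stands for cycle 1 prophylaxis. A reader might infer that Appendix 4 authorises G-CSF in cycle 1, but it never names cycle 1, so the point is an omission. The same argument is weaker for the restart dose. The Grade 3 row is also silent on growth factor, but it states a restart level, and that level is wrong under 8.6.1.4 once growth factor has been used. It does not resolve the LY3214996 cell, which is written for the growth-factor case itself.

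**An unchanged dose could mean suspend, then resume at the same level.** The neutropenia table offers some support: its LY3214996 cells all leave the dose unchanged, yet the note beneath suspends therapy. But the anemia table has no such note, its growth-factor row names abemaciclib alone, and where Appendix 4 wants LY3214996 held and restarted unchanged (Grade 2 nausea, for example) it says so. Continuing LY3214996 is the natural reading.

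**Section 8.6.1.4 may be about white-cell growth factors only.** The guideline it cites is listed in the references as covering those, and the red-cell guideline is cited only for transfusion. The intent is arguable. However, the wording is unqualified, and the anemia row applies the same suspension and reduction to abemaciclib.

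**The reach is limited.** Transfusion is an option for anemia, no Grade 3 or higher related anemia was reported in Part C in Table 3.2, and dose adjustments are reviewed weekly under Section 13. This is fair and keeps the point modest, but those at the weekly review would face the same two texts.

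**Conclusion.** The point holds, with its parts unequal. The LY3214996 cell in the anemia growth-factor row contradicts a mandatory rule. The first Grade 3 neutropenia row gives the wrong abemaciclib restart dose under 8.6.1.4 when growth factor is used. The missing cycle 1 limit is minor.

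The size is one abemaciclib dose step (33% at the starting dose) and at least two LY3214996 doses (400 mg) per affected patient. This assumes that 8.6.1.4 is the intended rule and that it covers growth factor given for anemia; the documents do not say which text is meant to govern.

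Three stronger readings are not supported:

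- A reader might take the 37.1% neutropenia rate as a guide to how many patients are affected. It comes from a different dose, a single agent and unstated grades, and says nothing about growth-factor use. The number cannot be estimated.
- A reader might infer that two reductions force abemaciclib to stop. Appendix 4 says that it should be discontinued only if a patient already at 50 mg Q12H needs a further reduction, and LY3214996 alone may continue.
- A reader might infer a threat to the primary analysis. The ORR definition, the success rule of 4 or more responses among 28 patients, type I error and power are unaffected. This is a matter of dosing and patient safety.

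**What to change.** Change Appendix 4 only, once the sponsor-investigator has confirmed that 8.6.1.4 is the intended rule:

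1. **Anemia table, growth-factor row, LY3214996 cell.** Replace the present entry with: suspend for at least 48 hours after the last growth-factor dose and until toxicity resolves to Grade 2 or less; resume at the same dose level. The recovery condition is the one in the adjacent abemaciclib cell and in the neutropenia note, so both drugs restart on one rule.
2. **Neutropenia table.** Add a row for G-CSF given to treat a neutropenia event: suspend both drugs on that same condition; resume abemaciclib one level lower unless already reduced for that event; resume LY3214996 at the same dose.
3. **Neutropenia note.** Limit the prophylactic G-CSF sentence to use after cycle 1, and state whether the abemaciclib reduction applies to prophylactic use. Without that statement, prophylaxis could be read as using up a dose step with no current toxicity.

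The cost is one changed cell, one new row and one completed note. Sections 8.6.1 and 8.6.1.4, the sample size, visits and analyses stay as they are.
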